7.2.3. Study Day

The study day is determined relative to the date of first dose of study treatment, unless otherwise specified. The day of the first dose of study treatment is defined as study day 1. The day prior to the first dose of study treatment is study day -1. There is no study day 0.

For events that occur before the first dose of study treatment,

study day = date of the event – first dose date;

for events that occur on or after the first dose of study treatment,

study day = date of the event – first dose date + 1.

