7.7. General Considerations for Efficacy during Induction Period

The Induction Period starts after the first injection of study treatment at Baseline Visit (Day 1) and ends prior to the first injection of study treatment at Week 16 or the early termination visit (ETV) (between Day 1 and Week 16). For patients who are randomized but not dosed, the Induction Period starts on the date of randomization.

For Pruritus Numeric Rating Scale (NRS) and Sleep-Loss due to Pruritus collected via eDiary, the baseline period is the 7-day window prior to the first injection. A patient must have responses on at least 4 of 7 days to calculate a baseline weekly mean. If a patient has 3 or fewer responses, the baseline mean value will be considered missing.

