Measure	Description	Variable	Derivation / Comment	Imputation Approach if Missing Components
		EASI 90	% Improvement in EASI score from baseline $\geq 90\%$: % change from baseline ≤ 90	Missing if baseline or observed value is missing.
		Time (in days) to EASI 50 (75) (90) up to week 16	Date of first time % change from baseline in EASI score ≥ 50 (75) (90) - date of W16 visit +1	If a patient has not experienced achievement of EASI 50 (75) (90) by completion or early discontinuation of Induction Period, the patient will be censored at the date of their last visit during Induction Period.
Investigator's Global Assessment (IGA)	The IGA is a static assessment and rates the severity of the patient's AD. The IGA is comprised of a 5-point scale ranging from 0 (clear) to 4 (severe) and a	IGA score	Single item. Range: 0 to 4 0 represents "clear" 4 represents "severe"	Single item, missing if missing.

This document is confidential.

Measure	Description	Variable	Derivation / Comment	Imputation Approach if Missing Components
	score is selected using descriptors that best describe the overall appearance of the lesions at a given time point.	IGA 0/1 with 2-point improvement	Observed score of 0 or 1 and change from baseline = -2	Missing if baseline or observed value is missing. Single item, missing if missing.
Body Surface Area (BSA)	The BSA assessment estimates the extent of disease or skin involvement with respect to AD and is expressed as a percentage of total body surface. BSA will be determined by the Investigator or designee using the patient palm = 1% rule	BSA score	BSA Total = BSAhead and neck + BSAtrunk + BSAupper extremities + BSAlower extremities	N/A – partial assessments cannot be saved.
		Change from baseline in BSA score	Change from baseline: observed BSA score – baseline BSA score	Missing if baseline or observed value is missing.
SCORing Atopic Dermatitis (SCORAD)		SCORAD score	SCORAD = A/5 + 7B/2 + C, where A is extent of disease, range 0-100 B is disease severity, range 0-18 C is subjective symptoms, range 0-20	Missing if component A or B or C is missing.

This document is confidential.

Measure	Description	Variable	Derivation / Comment	Imputation Approach if Missing Components

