Topical Corticosteroids (TCS)	Topical Corticosteroids (TCS) Diary records patient's treatment of Atopic Dermatitis with a TCS and the areas of application. Assessments will be recorded daily up to W2, weekly from W2 to W16, and every 4 weeks from W16 onward by the patient using an electronic diary.	Proportion of free days from baseline to week 16	Proportion of TCS-free days is calculated as the total number of days in study from baseline to Week 16 where TCS were not used, divided by the total number of days in study from baseline to Week 16.	If patient does not complete study until Week 16 then total number of days will be capped at the date of the last assessment in study

This document is confidential.

Measure	Description	Variable	Derivation / Comment	Imputation Approach if Missing Components
		Time to TCS-free days from baseline to week 16	Time to TCS-free days is calculated as the time from baseline to first point where TCS are not used or Week 16 + 1, whichever is the earlier.	If patient does not complete study to Week 16 then censor at the date of the last assessment in study
RECAP	
RECAP is a seven-item questionnaire designed to capture the experience of eczema control in all ages and eczema severities.
 
Each of the seven questions in RECAP carries equal weight and is scored from 0 to 4 (total score of 0-28).
	Change from Baseline in RECAP by week up to Week 16	
The total RECAP score is calculated as the sum of all question scores.
 
Change calculated for each post-baseline assessment as:
 $\text{observed RECAP total score} - \text{baseline RECAP total score}$	
If one question is left unanswered this is scored 0 and the scores are summed and expressed as usual out of a maximum of 28.
 
If two or more questions are left unanswered the questionnaire is not scored.
 
If two or more response options are selected, the response option with the highest score should be recorded

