9.4. Analysis of all Other Secondary and Other Efficacy Endpoint

The main and second estimands as described in Section 6.1.2 will be analysed by means of a mixed effect model for repeated measures (MMRM), including the Baseline value as a covariate, and adjusting by the factors of country, age (adolescents/adults), Baseline severity of disease (IGA=3/IGA=4), previous exposure to dupilumab (yes/no, when the overall population is analysed) and visit and treatment-visit interaction. A restricted maximum likelihood method will be specified, along with an unstructured covariance matrix. Estimates of the LS Means for each of the 2 treatment groups at each visit up to and including Week 16, along with the difference between treatments in LS Means, 2-sided 95% CI and p-value for the difference will be presented.

Example SAS syntax is as follows:

CCI

This document is confidential.

CCI

For all continuous secondary efficacy endpoints, in case of non-convergence, the country factor will be removed from the model.

Time-to-event (TTE) endpoints will be analysed on the second estimand for continuous endpoints using Kaplan-Meier survival analysis methods. If available, for descriptive purposes, the estimate of the median time-to-event (in weeks) and the 2-sided 95% CI will be presented. A comparison of the survival distribution curves for the 2 treatment groups will be made by means of the log-rank test. The Cox proportional hazards model will be used to estimate the hazard ratio and its 95% CI of lebrikizumab compared with placebo at the respective time point. The main Cox proportional hazards model will include treatment group, with country, age, Baseline disease severity and previous exposure to dupilumab (when the overall population is analysed) as factors. The proportional hazard assumption will be evaluated on all factors (ie, treatment and stratification factors) by graphical inspection of the Schoenfeld residuals and by Grambsch and Therneau test as well. Country may be removed from the model as appropriate, similar to the other analyses of efficacy. Because of the fact that the Induction and Maintenance Periods will be reported separately, TTE endpoints will be analysed at 2 separate time points: initially up to and including Week 16, and then separately for the whole study, incorporating both the Induction and Maintenance Periods.

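### SAP 9.2 measures time to EASI 50/75/90 from the Week 16 visit, so responses at earlier scheduled visits get negative times and responders who leave early get no time at all

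*SAP*

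**What the plan says.** In the EASI block of SAP 9.2, the derivation cell for time in days to EASI 50, 75 or 90 starts from the "Date of first time % change from baseline in EASI score" reaches 50, 75 or 90 or more, and subtracts the "date of W16 visit +1". The neighbouring cell deals with non-responders: "If a patient has not experienced achievement of EASI 50 (75) (90) by completion or early discontinuation of Induction Period", then "the patient will be censored at the date of their last visit during Induction Period". It names no origin.

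Three other places bear on the origin:
- SAP 7.2.3: "The study day is determined relative to the date of first dose of study treatment, unless otherwise specified". For events on or after first dose, study day is event date minus first dose date plus 1.
- SAP 9.2, TCS row: "Time to TCS-free days is calculated as the time from baseline to first point where TCS are not used", or Week 16 plus 1 if that is earlier.
- SAP 9.6, time-to-EASI row: estimand and method are both given as NA, and the analysis type is redacted.

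On analysis, SAP 9.4 states: "Time-to-event (TTE) endpoints will be analysed on the second estimand for continuous endpoints using Kaplan-Meier survival analysis methods". It adds a median in weeks, a log-rank test and a Cox model.

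**The concern.** A time-to-event variable needs an origin at or before the first moment at which the event can occur. The Week 16 visit is the last moment at which it can occur in this endpoint. Programmed as written, the formula gives negative times for almost all early responses and nothing for a responder who has no Week 16 visit. Censored patients have a date with nothing to subtract from it.

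The printed trigger also runs the wrong way. SAP 7.2.4 defines change as post-baseline minus baseline, so improvement is negative, and the EASI 50 and EASI 75 rows correctly use at most -50 and -75. A percentage change of 50 or more would be a worsening. The censoring cell shows that achievement of EASI 50/75/90 is meant, so the intent is not in doubt, but the cell should say so.

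At stake are the Kaplan-Meier curve, median, log-rank test and hazard ratio for time to EASI. No other endpoint uses this rule.

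**Working it through.** The plan gives no numerical result for this endpoint, so there is no figure to reproduce. The check applies the printed rule to the scheduled visits.

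**Inputs.** EASI is assessed after baseline at Weeks 2, 4, 8, 12 and 16 in the Induction Period (Protocol Table 1). SAP 7.4 gives target days 14, 28, 56 and 84 for the first four. Its table stops at Week 14 (day 98), so day 112 for Week 16 is an assumption (7 x 16). Let d be the number of days from first dose to the first visit with a response.

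**Formulas.** As printed: d - 112 + 1. From first dose, as in SAP 7.2.3: d + 1.

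| First response | d | As printed | From first dose |
|---|---|---|---|
| Week 2 | 14 | -97 | 15 |
| Week 4 | 28 | -83 | 29 |
| Week 8 | 56 | -55 | 57 |
| Week 12 | 84 | -27 | 85 |
| Week 16 | 112 | +1 | 113 |

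**Visit windows.** With ±3 days on both visits, each value before Week 16 moves by at most 6 days. Week 12 then runs from -33 to -21, so no sign changes. In general, a response two or more days before the Week 16 visit is negative, one day before is 0, and the same day is +1.

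**Early leavers.** SAP 7.7 ends the Induction Period at Week 16 or at an early termination visit. A patient who reaches EASI 75 at Week 4 and leaves at Week 10 has an event date but no Week 16 visit date, so the formula has no value.

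**Censored patients.** The SAP does not say that the event formula applies to them. If it did, a completer who never responds, censored at the Week 16 visit, would get +1, the same as a first response at that visit. If first dose were used for them instead, the same patient would be censored at 113 while events sat between -97 and +1. Neither gives a common time scale.

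**Does another section override the cell?** No. SAP 7.2.3 yields where something else is specified, and SAP 9.2 does specify something else. SAP 9.6 says NA. The TCS row covers a different endpoint.

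**The case against.** The strongest reply is that this is a drafting slip with an obvious intent. The row is labelled as time up to Week 16, negative durations would stand out, and SAP 14 provides for checks of program logic and output. Time to EASI appears in neither visible endpoint list. All of that stands, and it limits the consequence. It does not make the cell correct: Protocol 11.2 lets the SAP prevail over the protocol, and no other text supplies an origin.

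One could add that the log-rank test and the Cox model use only the order of times, and that for completers the printed rule is a shift of 112 days (15 minus -97). But the shift equals each patient's own Week 16 timing, 109 to 115 days within the ±3-day window, so order is only roughly kept. Early leavers and censored patients have no place in it. The median would also be meaningless: a Week 8 median would be -55/7 = -7.9 weeks.

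A reader might infer two stronger things, and the documents support neither.

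- **That the key secondary endpoints are misdefined.** In the text read here, the 9.2 cells show IGA change equal to -2, pruritus and skin-pain change at most 4, and EASI 90 percentage change at most 90. Each turns on one character, and this SAP text has evident misreads: the screening window in SAP 4.6 ends at Day +1 where Protocol Table 1 has Day -1, and the POEM row has 5 to 8 days where Protocol 10.4.8 has 5 to 6. Intent is clear from the row labels and SAP 9.6. For IGA, entry requires a score of at least 3, so any score of 0 or 1 is already an improvement of at least 2 points (3 - 1 = 2). This is a proofreading question.
- **That the number of patients affected can be worked out from the planned response rates.** The planned 55% and 30% are EASI 75 rates at Week 16. The event here is first achievement at any visit up to Week 16, and the documents give no rate for that.

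**Conclusion.** The derivation of time to EASI 50/75/90 is wrong as written. The error lies in the words naming the Week 16 visit, so a lost symbol cannot explain it. Followed literally, it gives -97, -83, -55 and -27 days for first responses at Weeks 2, 4, 8 and 12, and +1 at Week 16. It gives no value for responders without a Week 16 visit and no origin for censored patients. These values rest only on nominal visit days, with Week 16 taken as day 112.

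The primary analysis is untouched: the EASI 75 rule is printed with the correct sign, and SAP 7.9 makes the primary endpoint alone decide success. The point is worth correcting because SAP 9.4 plans formal comparisons of time-to-event endpoints, but it does not threaten the trial's main conclusion. How many patients would be affected cannot be estimated from the documents.

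**What to change.** Rewrite the cell in SAP 9.2:

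- **Event:** date of the first visit with percentage change from baseline in EASI of at most -50 (-75, -90), minus first dose date, plus 1.
- **Censored:** date of the last Induction Period visit, minus the same origin, plus 1.
- **Origin if not dosed:** randomisation date. The FAS includes all randomised patients, so first dose alone would leave some without an origin. SAP 7.7 and Appendix 1 already fall back to randomisation.

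At nominal visit days this gives 15, 29, 57, 85 and 113 days.

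As a proofreading step only, compare four other SAP 9.2 cells with the original PDF. If they are as read here, correct IGA to a change of at most -2, pruritus and skin pain to at most -4, and EASI 90 to a percentage change of at most -90.

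Cost: one SAP cell for certain and up to four more after the PDF check, before programming is finalised. No new data and no change to trial conduct.

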The use of TCS is prohibited for at least 1 week before the Baseline visit. A mid-potency TCS, triamcinolone acetonide 0.1% cream, and a low-potency TCS, hydrocortisone 1% cream (for use on sensitive skin areas), will be provided by the Sponsor or clinical site during the Induction Period only. The use of concomitant medications for other medical conditions (eg, hypertension, diabetes, acute infections) is permitted during this study.

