12.1.3 Patient Diary

A mobile application named the Study App will be used during the study. Research personnel will be instructed on the use of the Study App in order that they further instruct the patients at

the Screening visit and as many times as deemed necessary. Patients will also receive written instructions on the Study App use and reminders, including but not limited to, complete the questionnaires and diary during the study, and treatment dosing

The Study App data will be available for the site in real time through the Study App admin portal. The site will be able to follow the progress and compliance of the patient.

When an instrument is used by a patient or Investigator to transmit patient data elements directly to the eCRF, the patient or Investigator is the data originator and the eCRF is the source of data. If a process is used by which the patient or Investigator uses the instrument to transmit data to a technology service provider database, the service provider database is the source.

The Study App will allow patients completing the PRO questionnaires and a diary. The patients will be asked to have the Study App on their own mobile phone. There will also be the possibility to provide patients with a mobile phone, if necessary.

For this study, each patient will complete the following PROs through the ePRO module:

- SCORAD (only those questions addressed to patients)
- Pruritus NRS
- Sleep-loss
- Skin pain NRS
- DLQI or CDLQI
- WHO-5
- RECAP
- TSQM-9
- POEM

Patients will also record use of TCS and study drug intakes in the Patient Diary as applicable.

The Study App recording will be transferred to the database.

The Study App will work across all smartphones.

At the study end the Investigator will receive a CD/DVD/USB drive with the mobile application data (in PDF format) from the patients enrolled at his/her location. The Investigator will keep this CD with the rest of the original data for as long as required by local regulations. The mobile application files are relevant documentation for registration.

The mobile app data is the sole property of the Sponsor and should not be available in any form to third parties without the written permission of the Sponsor, except to authorise representatives of appropriate Competent Authorities.

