Body Surface Area (BSA)	Change from baseline in BSA score up to W16	Primary Estimand (Hybrid)	MMRM and BOCF	FAS	Key secondary analysis: Change from baseline in BSA score up to W16

This document is confidential.

Measure	Variable	Estimand (Section 6)	Analysis Method (Section 6.3)	Population (Section 5)	Analysis Type
SCORing Atopic Dermatitis (SCORAD)	Change from baseline in SCORAD score up to W16	Primary Estimand (Hybrid)	MMRM and BOCF	FAS	Key secondary analysis: Change from baseline in SCORAD score up to W16
Sleep-loss Score	Change from baseline sleep loss up to W16	Primary Estimand (Hybrid)	MMRM and BOCF	FAS	Key secondary analysis: Change from baseline sleep loss up to W16
Patient-Oriented Eczema Measure (POEM)	Change from baseline in POEM score	Primary Estimand (Hybrid)	MMRM and BOCF	FAS	Key secondary analysis: Change from baseline POEM up to W16
(Children) Dermatology Life Quality Index (DLQI/ CDLQI)	Change from baseline in DLQI total score up to W16	Primary Estimand (Hybrid)	MMRM and BOCF	FAS	Key secondary analysis: Change from baseline DLQI/ CDLQI up to W16
	Change from baseline in CDLQI total score up to W16	Primary Estimand (Hybrid)	MMRM and BOCF	FAS*	Key secondary analysis: achieving at least 4-point improvement in DLQI up to W16
	Proportion of patients achieving at least 4-point improvement in DLQI up to W16	Primary Estimand (Hybrid)	MMRM and BOCF	FAS*	Key secondary analysis: achieving at least 4-point improvement in DLQI up to W16

This document is confidential.

Measure	Variable	Estimand (Section 6)	Analysis Method (Section 6.3)	Population (Section 5)	Analysis Type
Topical corticosteroids (TCS)-free TCS data collected in CRF and not from eDiary.	Proportion of TCS-free days up to W16	Primary Estimand (Hybrid)	MMRM and BOCF	FAS	Key secondary analysis: Proportion of TCS-free days up to W16
	Time to TCS-free days up to W16	Primary Estimand (Hybrid)	Kaplan-Meier	FAS	Key secondary analysis: Time to TCS-free days up to W16
	Time to TCS-free days up to W16	Secondary Estimand (Composite)	Kaplan-Meier	FAS	Key secondary analysis: Time to TCS-free days up to W16
Skin Pain NRS	Change from baseline Skin Pain NRS up to W16	Primary Estimand (Hybrid)	MMRM and BOCF	FAS	Key secondary analysis: Change from baseline Skin Pain NRS up to W16
	Percentage of patients achieving a 4-point improvement Skin Pain NRS at W16	Primary Estimand (Hybrid)	MMRM and BOCF	FAS*	Key secondary analysis: Percentage of patients achieving a 4-point improvement Skin Pain NRS at W16

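### The SAP gives two conflicting data sources for TCS-free days, and its set-to-baseline rule would, on the SAP's own diary baseline, give treatment failures the best possible score

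*SAP*

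**What the plan says.** SAP 9.2 describes a TCS diary kept by the patient: the "Diary records patient's treatment of Atopic Dermatitis with a TCS and the areas of application". On frequency it says "Assessments will be recorded daily up to W2, weekly from W2 to W16, and every 4 weeks from W16 onward". The numerator of the endpoint is the "total number of days in study from baseline to Week 16 where TCS were not used". The denominator is every study day over the same period, whether or not it has a diary entry. For patients who leave early, the "total number of days will be capped at the date of the last assessment in study". Protocol 12.1.3 also places TCS recording in the diary: "Patients will also record use of TCS and study drug intakes in the Patient Diary as applicable".

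The SAP 9.6 summary table states, in the row for this measure, "TCS data collected in CRF and not from eDiary". The row assigns the proportion of TCS-free days to the primary (hybrid) estimand with MMRM and BOCF. SAP 6.1.2 defines that estimand for continuous secondary endpoints. Discontinuation for lack of efficacy (ICE2) and rescue or prohibited medication (ICE3) are set to baseline. SAP 9.4 adds the baseline value as an MMRM covariate.

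SAP 9.2 gives no baseline for this endpoint. The diary rule in SAP 7.2.4 is the mean of the 7 days before study treatment. Protocol 9.9.2 says of that week: "The use of TCS is prohibited for at least 1 week before the Baseline visit". Exclusion criterion 3 (Protocol 8.3) says the same.

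**The concern.** Two programmers following the SAP could build this variable from different data. SAP 11, which lists departures from the protocol, does not mention a change of TCS source.

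The second problem concerns direction. For EASI or itch, baseline is a bad state, so carrying it forward penalises failure. For TCS-free days, the pre-treatment week is a washout and so the best state on the scale. Set-to-baseline would credit a patient rescued with high-potency TCS with complete freedom from TCS. The steroid-sparing comparison would then be biased against whichever arm needs less rescue.

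**Working it through.** The documents give no expected value or power for this endpoint, so there is no stated figure to reproduce.

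**1. Source.** SAP 9.2 says electronic diary; SAP 9.6 says CRF and not eDiary. Both are current SAP text and cannot both hold.

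**2. What the diary could cover to Week 16.**
- Denominator: 16 × 7 = 112 days.
- Entries: 14 daily (to Week 2) + 14 weekly (Weeks 2 to 16) = 28.
- If a weekly entry describes one day: 28 / 112 = 25%, leaving 84 days without a status.
- If a weekly entry describes 7 days: 14 + 14 × 7 = 112, that is 112 / 112 = 100%.
- SAP 9.2 states neither the recall period nor how a day without a status counts.
- Under one-day recall, a patient using TCS on every recorded day scores 0 / 112 = 0% or 84 / 112 = 75%, depending on whether the other days count as use or as free. A patient free on every recorded day scores 28 / 112 = 25% or 112 / 112 = 100%.

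**3. The value given to treatment failures.**
- ICE2 and ICE3 are set to baseline (SAP 6.1.2, applied by the 9.6 row).
- Diary baseline is the mean of the 7 pre-treatment days (SAP 7.2.4), and TCS is banned in that week (Protocol 8.3 and 9.9.2).
- A compliant patient therefore has 7 / 7 = 100% at baseline, the maximum. The baseline covariate would also be constant among compliant patients and adjust for nothing.

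**4. Effect on the treatment difference.** Let r be the share of an arm with ICE2 or ICE3, and s the true TCS-free share in those patients, taken as equal in both arms. Setting them to 100% raises the arm mean by r × (1 − s), so

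shift (lebrikizumab − placebo) = (r_lebrikizumab − r_placebo) × (1 − s).

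The documents give no values for r or s, so every row is an assumption:

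| ICE2/3: lebrikizumab vs placebo | s | Shift (points) |
|---|---|---|
| equal rates | any | 0 |
| 5% vs 10% | 40% | −0.05 × 0.60 = −3.0 |
| 8% vs 20% | 20% | −0.12 × 0.80 = −9.6 |
| 10% vs 20% | 20% | −0.10 × 0.80 = −8.0 |
| 10% vs 30% | 20% | −0.20 × 0.80 = −16.0 |

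More rescue on lebrikizumab would reverse the sign.

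**The case against.** Several counter-arguments have force.

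- **Precedence.** Protocol 11.2 lets the SAP prevail over the protocol, so the protocol's diary statement does not by itself create an open conflict. That stands. The conflict between SAP 9.2 and 9.6 remains.
- **Coverage.** A reader might infer that three quarters of the days are unrecorded. The documents do not support that as a flat statement. It needs the diary as source, which 9.6 denies, and one-day recall, which is nowhere stated for TCS. CRF start and stop dates could classify every day. Whether they do is unclear: Protocol 9.9.2 requires such dates for nonstudy medications, while Induction TCS is supplied by the sponsor or site, used intermittently, and tracked by tube return (Protocol 9.5).
- **The 100% value.** A reader might infer that the SAP states that rescued patients score 100%. It does not. The value follows from combining SAP 9.6, 6.1.2 and 7.2.4 with the TCS ban. SAP 6.3.1.1, the operational BOCF text, refers only to death. If all of Day 1 served as baseline, the required start of TCS at Baseline (Protocol 7.1) would give about 0%. With the CRF as source, the 7-day diary rule does not plainly apply. These points show that the value is undefined. They do not make set-to-baseline suitable, because any pre-dose value in a compliant patient would most likely be TCS-free.
- **Template entry.** The 9.6 table also attaches MMRM with BOCF to binary responder endpoints that SAP 9.4 sends to the CMH method, so the entry may be a carry-over. It is still the stated method for this endpoint.

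**Conclusion.** The point holds in a limited form. The source contradiction inside the SAP is certain. The set-to-baseline rule has no defined value for this endpoint and, under the SAP's only diary baseline rule, rewards treatment failure. That 100% is an inference from the SAP's own rules and rests on compliance with the washout.

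The −9.6 points illustrate the mechanism under assumed rates and are not an estimate of bias in this trial; equal rates give zero. If lebrikizumab has less rescue, the error works against it and would not inflate its effect. The 28 of 112 figure is conditional on the diary source and one-day recall.

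The SAP 9.6 table labels this a key secondary analysis, which might suggest that the trial's main claims are affected. They are not. SAP 3 flags only IGA 0/1 and the 4-point pruritus response as key secondary, and SAP 7.9 rests study success on the primary endpoint alone. EASI 75 is untouched. Correction is advisable because a named secondary endpoint would otherwise be ambiguous in source and scored in the wrong direction for failures.

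**What to change.** 1. Name one source in both SAP 9.2 and 9.6, and record it in SAP 11 if it departs from the protocol. Use CRF start and stop dates if they cover the supplied TCS on all days.
2. Remove BOCF and the baseline covariate for this endpoint.
3. Count days of rescue TCS as TCS use. Patients on high-potency TCS stay in the study (Protocol 9.9.4), so their use can be observed.
4. In line with the composite strategy, score days after ICE2 or systemic rescue as not TCS-free. Reconcile this with the 9.2 cap at the last assessment, which would otherwise drop those days from the denominator.
5. If the diary is kept as source, state the recall period. Compute the share within each week on days of known status, then average over the 16 weeks. Pooling recorded days under one-day recall would give Weeks 0 to 2 a weight of 14 / 28 = 50%, although they are 14 / 112 = 12.5% of the period and TCS is started at Baseline by requirement. Weekly averaging restores 2 / 16 = 12.5%.

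The cost is SAP wording and derivation code, with no new data collection. Under one-day recall, each later week would rest on one entry, so individual values would be coarse.
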